- To demonstrate efficacy of AB103 in relation to the critical care and hospital stay parameters:
 - a. ICU days
 - b. ICU-free days
 - c. Days on ventilator
 - d. Ventilator free days
 - e. Vasopressor days
 - f. Vasopressor free days
 - g. Hospital length of stay
- To demonstrate the efficacy of AB103 in patients with septic shock
- To determine the incidence of Stage 2 and 3 acute kidney injury (AKI) (using the KDIGO criteria) and compare the rates of complete recovery by Day 28 between the AB103 treated patients and the placebo treated patients
- Additional AKI endpoints:
 - To determine the incidence of Stage 2 and 3 AKI (using the KDIGO criteria) and compare the rates of complete and partial recovery by Day 28 between AB103 and placebo treated patient
 - Determine the incidence of Stage 1, 2 and 3 AKI and compare the rates of complete recovery between the AB103 and placebo treated patients
 - Determine the incidence of Stage 1, 2 and 3 AKI and compare the rates of complete and partial recovery between the AB103 and placebo treated patients
 - Calculate time to complete recovery from AKI
 - Calculate time to partial recovery from AKI
- To demonstrate the safety of AB103 in regard to secondary infections

2.3 Exploratory Objectives:

- To conduct an exploratory evaluation of the clinical response by baseline pathogen
- To evaluate microbiological outcome in the microbiological evaluable population
- To conduct an exploratory evaluation of plasma and urinary biomarkers in patients with AKI
- To conduct an exploratory evaluation of blood leukocyte transcriptome (RNA expression) profiling in patients with NSTI and compare genomic profile in patients treated with AB103 versus placebo
- To evaluate health economic and financial outcomes associated with the treatment
- To evaluate NICCE outcome in screen failure patients with baseline mSOFA = 2 and post-operative mSOFA \ge 3. Note: These patients will not be included in the

MITT population analysis (they will not receive blinded study drug) and only considered to be an observational cohort

• To evaluate the immunogenicity of Reltecimod (formerly AB103)

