4.1.3 Other AKI Endpoints

Exploratory AKI endpoints include the primary endpoint evaluated at Day 14, improvement in durable loss of renal function defined as alive, free of dialysis and improvement leading to a lower AKI stage but no better than Stage 1 AKI evaluated at Day 14 and Day 28, and AKD stage evaluated at Day 14 and Day 28.

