4.1.4.2 Screening AKI and Screening eGFR

Screening (pre-dose) AKI will be determined by comparing screening (pre-dose) creatinine to the algorithmic determination of reference as described in Exhibit 1 based on the rules summarized in Exhibit 2.

Exhibit 2. Algorithmic Determination of Screening (pre dose) AKI Stage						
Stage	Serum Creatinine					
0	<1.5 times reference					
1	1 1.5 to <2.0 times reference					
2 ≥2 to 3 times reference						
3	≥ 3 times reference OR Increase in serum creatinine to ≥4 mg/dL OR Initiation of renal replacement therapy					
Reference may be either algorithmically determined or independently adjudicated depending on analysis.						

Screening eGFR will be determined using the following formula.

Screening eGFR (mL/min/1.73 m²) = $175 \times (Screening Cr)^{-1.154} \times (Age)^{-0.203} \times (0.742 if female) \times (1.212 if African American).$

As a sensitivity analysis, when determining AKI endpoints, the adjudicated reference creatinine will be used in place of the algorithmically determined reference value.

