4.1.4.4 Day 14 eGFR

Day 14 eGFR will be determined by converting Day 14 creatinine to Day 14 eGFR using the following formula:

Day 14 eGFR (mL/min/1.73 m²) = $175 \times (Cr Day 14)^{-1.154} \times (Age)^{-0.203} \times (0.742 if female) \times (1.212 if African American).$

Percentage loss in eGFR at Day 14 will be determined using the following formula.

Percentage loss in eGFR at Day 14 = 100% times [Screening eGFR - (Day 14 eGFR) / Screening eGFR]. If percentage loss $\ge 37\%$ then patient fails the Day 14 endpoint.

4.1.4.5 Determining AKD Stage at Day 28

Exhibit 2 will also be used to determine AKD Stage at Day 28 except that the criterion for renal replacement therapy is an ongoing need rather than initiation.

4.1.4.6 Determining AKD Stage at Day 14

Similarly, Exhibit 2 will be used to determine AKD Stage at Day 14 except that the criterion for renal replacement therapy is an ongoing need rather than initiation.

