8.11 Freedom from Durable Loss of Renal Function

Tables 14.2.6.1.1 to 14.2.6.6 summarize AKI at pre-dose screening and Maximal AKI determined over the first seven days though independent adjudication.

Tables 14.2.6.2.1 to 14.2.6.2.4 summarize treatment group comparisons of the AKI endpoints at Day 28 including the key secondary endpoint, *Achieving Freedom from Durable Loss of Renal Function at Day 28* and the exploratory endpoint, *Improvement in Durable Loss of Renal Function at Day 28*. The summarized analyses differ with regard to whether there was algorithmic determination (primary) or independent adjudication of reference creatinine (sensitivity analysis) and whether the algorithmic determination of Day 28 status was based on LOCF (primary) or using the mean value over days 14 to 28 (sensitivity analysis). The results from Table 14.2.6.2.1 will contain the results from the key secondary endpoint.

Tables 14.2.6.3.1 to 14.2.6.3.3 summarize treatment group comparisons of the AKI endpoints at Day 14 including *Achieving Freedom from Durable Loss of Renal Function at Day 14* and *Improvement in Durable Loss of Renal Function at Day 14*. The summarized analyses differ with regard to whether there was algorithmic determination or independent adjudication of reference creatinine and whether there was algorithmic or independent adjudication of Day 14 status.

Figure 39 will graphically summarize the percentages of subjects in each group achieving *Freedom from Durable Loss of Renal Function* at Days 14 and 28. Similarly, Figure 40 will graphically summarize the percentages of subjects in each group achieving *Improvement in Durable Loss of Renal Function* at Days 14 and 28.

Tables 14.2.6.4.1 to 14.2.6.4.2 summarize treatment group comparisons of AKD stage at Day 28. The summarized analyses differ with regard to whether there was algorithmic determination or independent adjudication of reference creatinine.

Tables 14.2.6.5.1 to 14.2.6.5.3 summarize treatment group comparisons of AKD stage at Day 14. The summarized analyses differ with regard to whether there was algorithmic determination or independent adjudication of reference creatinine and whether Day 14 status was determined algorithmically or through independent adjudication.

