35	Critical care and hospital stay	Line graph	% of patients needing ventilation over time by treatment group	Figure35.sas
36	Critical care and hospital stay	Line graph	% of patients staying at Hospital over time	Figure36.sas
37	Debridement	Bar chart with mean (SD)	Cumulative Numbers of Debridements to Days 7, 10, 14, and 28 Overall and by Treatment Group By Treatment Group	Table 14.2.5.1
38	Debridement	Bar graphs with %'s and Fisher's p-values.	Percentages of Patients Requiring 1, 2, ≥ 2, and ≥ 3 Debridements Though Day 14, By Treatment Group	Table 14.2.5.2
39	AKI	Bar graph	Percent of patients Achieving Freedom from Durable Loss of Renal Function	Table 14.2.6.2.1 Table 14.2.6.3.1
40	AKI	Bar graph	Percent of patients Achieving Improvement in Durable Loss of Renal Function at Day 14 and at Day 28	Table 14.2.6.2.1 Table 14.2.6.3.1
41	Mortality	Kaplan-Meier	Mortality to Day 90	Table 14.3.8.1 Table 14.3.8.2
42	Mortality	Kaplan-Meier	Mortality from Day 14 to Day 90 Comparing mSOFA<=1 at Day 14 to mSOFA>1 at Day 14 - Pooled	Table 14.3.8.3
43	Mortality	Kaplan-Meier	Mortality from Day 14 to Day 90 Comparing mSOFA<=1 at Day 14 to mSOFA>1 at Day 14 - Reltecimod	Table 14.3.8.4
44	Mortality	Kaplan-Meier	Mortality from Day 14 to Day 90 Comparing mSOFA<=1 at Day 14 to mSOFA>1 at Day 14 - Placebo	Table 14.3.8.5
45	NICCE and Components	Forrest Plot	99% CI for NICCE and 95% CI's for Components of NICCE	Table 14.2.1.1
46	Conditional Co- Primary and Components	Forrest Plot	95% CI for conditional co-primary and components	Table 14.2.1.2
47	NICCE	Forrest Plot	Point estimates and 95% CI for NICCE in subgroups	Stratified versions of Table 14.2.1.1
48	ССРЕ	Forrest Plot	Point estimates and 95% CI for CCPE in subgroups	Stratified versions of Table 14.2.1.2
49	AKI endpoint	Forrest Plot	Point estimates and 95% CI for AKI endpoint in subgroups	Stratified versions of Table 14.2.6.3

15 Appendix 5: Clinical Score Calculations

Clinical Scores Parameters					
Parameter	LRINEC	Anaya	SOFA		
Clinical					
Cardiovascular system (Mean Arterial Pressure calculation)			+		
Heart Rate		+			
Nervous system (Glasgow Coma Score)			+		
Oxygenation (Calculation)			+		
			(PaO ₂ /FiO ₂)		
Temperature		+			
Demographics					
Age		+			
Laboratory					
Coagulation Function (Platelets)			+		
C-Reactive Protein	+				
Renal system / Creatinine	+	+	+		
Glucose	+				
Hemoglobin/Hematocrit	+	+			
Liver Function Test / Bilirubin			+		
Sodium	+				
Total white cell count	+	+			

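### The exploratory renal improvement endpoint scores full recovery as no improvement, so its between-arm comparison can point against a beneficial drug

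*SAP*

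**What the plan says.** SAP 4.1.3 lists the endpoint among the exploratory ones ("Exploratory AKI endpoints include the primary endpoint evaluated at Day 14, improvement in durable loss of renal function") and defines it as "alive, free of dialysis and improvement leading to a lower AKI stage but no better than Stage 1 AKI", assessed at Days 14 and 28.

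Exhibit 2 in SAP 4.1.4.2 supplies the stages. Stage 0 is creatinine "<1.5 times reference" and Stage 1 is "1.5 to <2.0 times reference". SAP 4.1.4.5 carries the staging forward: "Exhibit 2 will also be used to determine AKD Stage at Day 28". SAP 4.1.4.6 does the same for Day 14. A patient can therefore end in a stage better than Stage 1.

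SAP 8.11 plans treatment-group comparisons that include improvement in Tables 14.2.6.2.1 to 14.2.6.2.4 (Day 28) and 14.2.6.3.1 to 14.2.6.3.3 (Day 14). The table titles give the population as mITT patients with Stage 2 or 3 AKI at screening. Improvement also gets a chart of its own: "Figure 40 will graphically summarize the percentages of subjects in each group achieving" this endpoint, listed in SAP Appendix 4 as "Percent of patients Achieving Improvement in Durable Loss of Renal Function at Day 14 and at Day 28".

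Protocol 2.2 includes, among its additional AKI endpoints, an objective to "compare the rates of complete and partial recovery by Day 28", that is, complete and partial recovery together.

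**The concern.** The population starts in Stage 2 or 3, and the best outcome available to it is a return to Stage 0. The cap leaves that outcome out of the numerator, and nothing in the SAP adds these patients back or takes them out of the denominator. A drug that moves patients from partial to full recovery therefore takes successes away from an endpoint called improvement.

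The risk is one of interpretation. SAP 1.1 says that the AKI results of this trial are meant to support those of ATB-203. A stand-alone improvement chart that favoured placebo because more treated patients had recovered fully would mislead its readers.

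**Working it through.** The documents give no expected rate, sample size or power for this endpoint, so there is no stated figure to reproduce.

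**Step 1: score each transition.** The inputs are the SAP 4.1.3 wording, the Exhibit 2 stages, and a start in Stage 2 or 3. The patient is taken to be alive and off dialysis at the end.

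| Start to end | SAP 4.1.3 | Any lower stage |
|---|---|---|
| 2 to 0 | fail | success |
| 2 to 1 | success | success |
| 2 to 2 or 3 | fail | fail |
| 3 to 0 | fail | success |
| 3 to 1 | success | success |
| 3 to 2 | success | success |
| 3 to 3 | fail | fail |

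The two rules differ only for 2 to 0 and 3 to 0. Under the SAP rule, the best outcome scores the same as no change.

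**Step 2: direction under a real benefit.** Let F be the full-recovery rate and A the any-recovery rate. The SAP endpoint is A − F and the uncapped endpoint is A. The drug is assumed to multiply the odds of both F and A by a common odds ratio (OR): p' = OR·o/(1 + OR·o), with o = p/(1 − p). All rates and odds ratios here are assumptions.

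One case in full, with placebo F = 40%, A = 70% and OR = 2:
- F' = 1.333/2.333 = 57.1%
- A' = 4.667/5.667 = 82.4%
- SAP endpoint: placebo 70 − 40 = 30.0%, drug 82.4 − 57.1 = 25.2% (from unrounded values), difference −4.8 points
- Uncapped endpoint: 82.4 − 70.0 = +12.4 points

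The full range, as drug minus placebo in percentage points for OR 1.5 / 2 / 3:

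| Placebo full/any recovery | SAP endpoint | Uncapped endpoint |
|---|---|---|
| 20%/50% | +2.7 / +3.3 / +2.1 | +10.0 / +16.7 / +25.0 |
| 30%/60% | +0.1 / −1.2 / −4.4 | +9.2 / +15.0 / +21.8 |
| 40%/70% | −2.2 / −4.8 / −9.2 | +7.8 / +12.4 / +17.5 |
| 50%/80% | −4.3 / −7.8 / −12.7 | +5.7 / +8.9 / +12.3 |
| 60%/85% | −4.8 / −8.1 / −12.4 | +4.5 / +6.9 / +9.4 |

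The SAP endpoint falls whenever the move from partial to full recovery exceeds the move from no recovery to partial. In these scenarios that happens at every odds ratio once placebo full recovery is 40% or more.

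**Step 3: relation to the key secondary endpoint.** Freedom from durable loss of renal function requires less than a 37% loss of eGFR. With the SAP's creatinine exponent of −1.154:
- a 37% loss corresponds to a creatinine ratio of 0.63^(−1/1.154) = 1.492
- a ratio of 1.5, where Stage 1 begins, corresponds to a loss of 1 − 1.5^(−1.154) = 37.4%

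If loss is measured from the reference value, as SAP 2.3 and 4.1.1 define it, freedom nearly coincides with ending alive, off dialysis and in Stage 0. The formula in SAP 4.1.4.3 instead measures loss from screening eGFR. On that formula, any fall in creatinine after screening gives a negative loss. A surviving, dialysis-free patient who goes from Stage 3 to Stage 1 then meets both freedom and improvement.

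**The case against.** The strongest defence is that the capped category was meant as partial recovery, to be read beside freedom. On the reference-based definition, freedom, improvement and neither divide patients almost exactly into full, partial and no recovery; only creatinine ratios between 1.492 and 1.5 fall in a gap. Both rates sit in the same tables, and Figures 39 and 40 form a pair. SAP 8.11 also compares AKD stage between arms at Day 28 (Tables 14.2.6.4.1 and 14.2.6.4.2) and Day 14 (14.2.6.5.1 to 14.2.6.5.3), where a shift from Stage 1 to Stage 0 would show. SAP 1.1 declares that the AKI endpoints were harmonised with ATB-203.

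Much of this stands, and it limits the harm. It does not remove the problem: the SAP never says that the endpoint is a partial-recovery category, names it improvement, and charts it alone.

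A reader might go further and infer that the SAP drops the protocol's complete-plus-partial objective. The documents do not support that. No passage says that improvement replaces it, SAP 5.7 still lists AKI recovery among the descriptive secondary endpoints, and combined recovery can be partly reconstructed from the freedom rate and the stage tables. What is missing is a single prespecified endpoint that combines the two.

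A reader might also infer that freedom and improvement are mutually exclusive. That holds only on the reference-based definition, not on the screening-based formula. The conflict between those two definitions is a separate matter, and the Stage 0 exclusion does not depend on it.

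**Conclusion.** The point holds as a low-severity defect in an exploratory endpoint. As written, full recovery from Stage 2 or 3 is scored as not improved, and the between-arm comparison can point the wrong way. In the scenarios examined, the difference on the SAP endpoint ranges from +3.3 to −12.7 points, while the uncapped endpoint favours the drug throughout. The scoring result follows from the text alone. The size and direction rest on assumed recovery rates and a common odds ratio.

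It would be too strong to infer that an effective drug will look worse. With 20%/50% placebo recovery the SAP endpoint still favours the drug, and with 30%/60% at the smallest odds ratio it is about neutral.

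SAP 5.6 plans no type 1 error control for this endpoint, and no success criterion uses it. The primary, co-primary and key secondary tests are unaffected.

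**What to change.** In SAP 4.1.3, define the compared endpoint as alive, free of dialysis and in any AKI stage lower than at screening, including Stage 0. Use it in Tables 14.2.6.2.1 to 14.2.6.2.4 and 14.2.6.3.1 to 14.2.6.3.3 and in Figure 40. Keep the capped category as a descriptive row beside full recovery, labelled *partial recovery only*, without a group comparison of its own.

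The cost is a change of SAP wording and one derived variable, with no new data. It should be made before unblinding. The downside is that the compared endpoint may then differ from the one of the same name in ATB-203, whose definition these documents do not give in full. The partial-only row preserves the link.

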4.1.4 Algorithmic Determinations

4.1.4.1 Reference

Exhibit 1 summarizes the algorithmic determination of reference creatinine. The algorithmic determination of baseline AKI stage will be based on comparing screening creatinine to the reference creatinine determined by Exhibit 1.

Exhibit 1. Algorithmic Determination of Reference Creatinine

Pre processing step:

Creatinine values obtained within 2 days of dosing will be handled as follows:

If there is only one value, this value will be excluded as input to the algorithm below.

If there are more than one value, compare the maximum to the minimum, and if within 25%, then all values will be included as input to the algorithm below. If greater than 25%, then the values obtained within 2 days will be excluded as input to the algorithm below.

This table indicates the rules to be used to determine reference creatinine based on the numbers of historical values available during the last 3 months prior to screening and available 4 to 12 months prior to screening. In general, the algorithm prioritizes use of historical creatinine values obtained within the last 3 months.

Number of last 3 month values	Number of 4 to 12 months	Rule	
0	0 Use MDRD to determine reference creatinine.		
0	1	Use the 4 to 12 month value.	
0 >=2		Use median of 4 to 12 month values.	
1	0	Use <=3 month value.	
>=2	>=0	Use median of <=3 month values.	
1	1	Use the mean of the two available values.	
1	>=2	Use the median of all available values.	
>=2	1	Use the median of all available values.	

The SAS code used to implement the MDRD formula^{5,6} to determine a reference creatinine when no historical values are available is:

```
if sex='Male' and black=0 then do;

t1 = der_age**(-0.203);

t2 = 1;

t3 = 1;

t4 = 186 * t1 *t2 *t3;

Scrt = (75 / t4)**(-0.887);

end;
```

⁵ Levey AS, Bosch JP, Lewis JB, Greene T, Rogers N, Roth D; Modification of Diet in Renal Disease Study Group. A more accurate method to estimate glomerular filtration rate from serum creatinine: a new prediction equation. Ann Intern Med 1999 Mar;130(6):461-470.

⁶ Levey AS, Greene T, Kusek I, Beck G. A simplified equation to predict glomerular filtration from serum creatinine (Abstract). J Am Soc Nephrol 2000;11:155A]

```
if sex='Female' and black=0 then do;
  t1 = der age**(-0.203);
    t2 = 0.742;
    t3 = 1:
    t4 = 186 * t1 * t2 * t3;
     Scrt = (75 / t4) **(-0.887);
     end;
if sex='Male' and black=1 then do;
    t1 = der age**(-0.203);
    t2 = 1;
    t3 = 1.21;
    t4 = 186 * t1 * t2 * t3;
     Scrt = (75 / t4)**(-0.887);
     end;
if sex='Female' and black=1 then do;
  t1 = der age**(-0.203);
    t2 = 0.742;
    t3 = 1.21;
    t4 = 186 * t1 * t2 * t3;
     Scrt = (75 / t4)**(-0.887);
    end;
```

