2.3 Key Secondary AKI Endpoint

The same endpoint that is being currently employed in the ongoing ATB-203 study of AKI in sepsis will be evaluated as the key secondary endpoint in this study. The key secondary endpoint is *freedom from durable loss of renal function at Day 28*. Only subjects with AKI Stage 2 or Stage 3 prior to initial drug dosing will be included in this comparison. The key secondary endpoint requires:

- (i) Alive at Day 28,
- (ii) Free of dialysis at Day 28, and
- (iii) Less than a 37% loss of estimated Glomerular Filtration Rate (eGFR; measured with the Modification of Diet in Renal Disease (MDRD) formula from the patient's reference eGFR)) at Day 28.

Reference creatinine values, baseline AKI stage and percentage loss of eGFR at Day 14 and 28 will be determined through algorithmic determination (see details below). Percentage loss of eGFR determined algorithmically will be based on a comparison of eGFR at screening compared to an algorithmically determined reference creatinine value. A sensitivity analysis will utilize an independently adjudicated reference value to determine baseline eGFR.

To control type 1 error for the key secondary efficacy endpoint, superiority of Reltecimod relative to placebo in terms of freedom from durable loss of renal function at Day 28 among those presenting with Stage 2 or Stage 3 AKI will only be interpreted as a confirmatory hypothesis test if $p \le 0.01$ for the primary endpoint (NICCE) and $p \le 0.05$ for the co-primary endpoint (CCPE).

Otherwise, treatment group comparisons in terms of the key secondary efficacy (AKI) endpoint will be interpreted as a descriptive endpoint. An unadjusted chi-square test using a two-sided type 1 error of α =0.05 will be used to test superiority of Reltecimod relative to placebo for the key secondary AKI endpoint.

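### Two rows of the reference-creatinine table (SAP Exhibit 1) give different rules for the same patients, which can decide entry to the key secondary kidney analysis

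*SAP*

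**What the plan says.** Exhibit 1 in SAP 4.1.4.1 has eight rows, indexed by how many historical creatinine values a patient has in the 3 months before screening (recent) and at 4 to 12 months (older). Two rows matter here:

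- Fifth row, two or more recent and zero or more older: "Use median of <=3 month values".
- Last row, two or more recent and exactly one older: "Use the median of all available values". The same words also appear for one recent and two or more older values, where they cause no difficulty.

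The text above the table says: "In general, the algorithm prioritizes use of historical creatinine values obtained within the last 3 months". No row order or tie-break is given.

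The reference is then used for staging: "The algorithmic determination of baseline AKI stage will be based on comparing screening creatinine to the reference creatinine determined by Exhibit 1". Exhibit 2 (SAP 4.1.4.2) defines Stage 2 as "≥2 to 3 times reference". Stage 3 begins at three times the reference and has two routes that do not use the reference: "Increase in serum creatinine to ≥4 mg/dL OR Initiation of renal replacement therapy". For the key secondary endpoint, SAP 2.3 states: "Only subjects with AKI Stage 2 or Stage 3 prior to initial drug dosing will be included in this comparison". The main analysis uses the algorithmic reference. The adjudicated one is secondary: "A sensitivity analysis will utilize an independently adjudicated reference value to determine baseline eGFR".

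**The concern.** A patient with two or more recent values and exactly one older value satisfies both rows, and the rows prescribe different calculations. This is a contradiction in a stated rule, not a missing detail. Two programmers working faithfully from Exhibit 1 could obtain different references for the same patient.

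The last row also sits badly with the rest of the table. It departs from the stated preference for recent values. It also lets a single older value count while two or more older values are ignored, because a patient with two or more of each meets only the fifth row.

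At stake is who enters the main key secondary comparison, which is confirmatory only if NICCE gives p≤0.01 and CCPE gives p≤0.05 (SAP 2.3 and 5.6). Screening AKI stage also feeds the AKI subgroups (SAP 4.6) and a covariate in the repeated-measures model for mSOFA (SAP 5.8). The reference enters AKD stage at Days 14 and 28 as well (SAP 4.1.4.5 and 4.1.4.6).

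**Working it through.** The documents give no sample size, power or event count for the key secondary endpoint, so there is no plan figure to reproduce. The check is of the rule table itself.

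**Step 1: coverage.** Number the rows of Exhibit 1 from 1 to 8 in printed order and list which rows match each pair of counts.

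| Recent values | 0 older | 1 older | 2 older | 3 older |
|---|---|---|---|---|
| 0 | 1 | 2 | 3 | 3 |
| 1 | 4 | 6 | 7 | 7 |
| 2 | 5 | **5 and 8** | 5 | 5 |
| 3 | 5 | **5 and 8** | 5 | 5 |

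Of the 16 combinations, 14 match exactly one row. The pairs (2,1) and (3,1) match two. There are no gaps.

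**Step 2: effect on stage.** Ratio = screening creatinine / reference, and the patient enters the analysis by ratio if it is at least 2. The creatinine values below (mg/dL) are assumed for illustration; none comes from the documents.

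| Recent | Older | Screening | Row 5: reference, ratio | Row 8: reference, ratio |
|---|---|---|---|---|
| 0.8, 1.0 | 1.4 | 1.9 | 0.9; 1.9/0.9 = 2.11, Stage 2, in | 1.0; 1.9/1.0 = 1.90, Stage 1, out |
| 0.8, 1.2 | 0.7 | 1.8 | 1.0; 1.8/1.0 = 1.80, Stage 1, out | 0.8; 1.8/0.8 = 2.25, Stage 2, in |
| 0.8, 0.9, 1.2 | 0.7 | 1.75 | 0.9; 1.75/0.9 = 1.94, Stage 1, out | 0.85; 1.75/0.85 = 2.06, Stage 2, in |
| 1.0, 1.0 | 0.7 | 1.9 | 1.0; 1.90, Stage 1, out | 1.0; 1.90, Stage 1, out |
| 0.8, 1.2 | 0.7 | 4.2 | Stage 3, in | Stage 3, in |

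Membership can change in either direction, and sometimes does not change at all. It changes only when screening creatinine is at least twice the smaller reference and below twice the larger. In the first example that window is 2 × 0.9 = 1.8 up to, but not including, 2 × 1.0 = 2.0 mg/dL.

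**Step 3: the odd treatment of older values.** In the first example, row 8 gives a reference of 1.0 with one older value of 1.4. Add a second older value of 1.4 and only row 5 applies, so the reference falls back to 0.9. Extra older information removes the influence of the first older value.

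**Step 4: rough size among patients with this pattern.** Assume log-normal within-patient variation with SD 0.10 to 0.30 on the log scale, two to four recent values plus one older value, and a screening-to-true-baseline ratio that is log-uniform from 1 to 4. In simulation, membership then changes for about 1.8% (SD 0.10, four recent) to 9.1% (SD 0.30, two recent). Among those with a true ratio of 1.6 to 2.4 the range is about 6% to 21%. The share of trial patients with the pattern cannot be derived from the documents.

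**The case against.** The strongest reply is that this is a small ambiguity with the likely answer in view. The sentence about recent values points to the fifth row. An adjudicated reference is planned as a sensitivity analysis, and Table 14.2.6.2.2 applies it to the population as well as to the endpoint, so dependence of membership on the Exhibit 1 reference will be examined. Only patients near the cut-off can change. NICCE and CCPE do not use Exhibit 1, and the formula for percentage loss in SAP 4.1.4.3 starts from screening eGFR, so as written that calculation does not move either.

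Most of this stands as a limit on size. It does not remove the contradiction. The preference for recent values is expressly only general, and the last row could have been meant as a specific exception to it. The adjudicated analysis does not settle the denominator of the main analysis. The protocol has no reference-creatinine algorithm to fall back on.

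A misprint is also possible. But if the older-value cell of the fifth row were meant to read 0, patients with two or more of each kind would have no rule, so the table would still need correction.

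A reader might go further and infer that the row would be chosen after the results are known, or that the overlap tilts the comparison. The documents do not support that. The SAP is to be finalised before unblinding (Section 1), its Version 4.0 changes were made blinded (Section 1.1), and the primary statistician sees only blinded data (Protocol 9.1.4). Neither row uses treatment assignment.

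**Conclusion.** The contradiction is real and minor. Exhibit 1 assigns two incompatible rules to patients with two or more recent values and exactly one older value, and the choice can put a patient inside or outside the main key secondary analysis. That this can happen rests only on the printed rows and cut-offs; how often it happens rests on assumption. The 1.8% to 9.1% range applies only to patients with this pattern and depends on the assumed variation and ratio distribution. Patients at 4 mg/dL or more, or started on renal replacement therapy, are Stage 3 under either row. There is no basis for expecting bias towards either arm, and the trial's overall success criterion is untouched. What is lost is a single reproducible definition of a population that may carry a confirmatory test.

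**What to change.** Before unblinding, make the rows of Exhibit 1 mutually exclusive. The simplest change is to delete the last row (two or more recent, one older). The remaining seven rows then cover every pair of counts exactly once and agree with the stated preference for recent values. If the sponsor intended the last row as an exception, narrow the fifth row to exclude exactly one older value and state why one older value counts when two or more do not. Since SAP 1.1 says the AKI endpoints are harmonised with ATB-203, confirm that the chosen rule matches the one used there; that algorithm is not in these documents.

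The cost is a one-line edit and a matching check of the derivation program. No new data are needed, and sample size and the alpha structure do not change.

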4.1.4.3 Day 28 eGFR

Day 28 eGFR will be determined by converting Day 28 creatinine to Day 28 eGFR using the following formula:

Day 28 eGFR (mL/min/1.73 m²) = $175 \times (\text{Cr Day } 28)^{-1.154} \times (\text{Age})^{-0.203} \times (0.742 \text{ if female}) \times (1.212 \text{ if African American}).$

Percentage loss in eGFR at Day 28 will be determined using the following formula.

Percentage loss in eGFR at Day 28 = 100% times [Screening eGFR - (Day 28 eGFR) / Screening eGFR]. If percentage loss $\geq 37\%$ then patient fails key secondary endpoint.

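### The imputed reference creatinine uses MDRD constant 186 while every eGFR formula uses 175, so imputed references run about 5–6% high against the SAP's own equation and raise the Stage 2 entry cut-off for the key secondary analysis

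*SAP*

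**What the plan says.** Exhibit 1 in SAP 4.1.4.1 gives the rule for a patient with no creatinine in the 3 months before screening and none at 4 to 12 months: "Use MDRD to determine reference creatinine". A lone value within 2 days of dosing is discarded before the rule is applied. Several values in that window are kept only if they agree within 25%.

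The SAS code "to determine a reference creatinine when no historical values are available is" given in four blocks, one for each combination of sex and race term. Each block forms t4 from 186, age to the power −0.203, a sex factor (1 or 0.742) and a race factor (1 or 1.21). It then computes "Scrt = (75 / t4)(-0.887", with the exponent applied to the ratio 75/t4.

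The three forward equations use a different constant. Screening eGFR begins "175 \times (Screening Cr)^{-1.154} \times (Age)^{-0.203". Day 28 and Day 14 eGFR have the same form, and all three use a race factor of 1.212. The SAP refers to both directions as MDRD and does not explain the two constants.

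The reference then feeds Exhibit 2 (SAP 4.1.4.2), which stages AKI by screening creatinine relative to reference. Stage decides entry to the key secondary comparison (SAP 2.3): "Only subjects with AKI Stage 2 or Stage 3 prior to initial drug dosing will be included in this comparison". Exhibit 2 is reused for AKD stage at Days 14 and 28.

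**The concern.** A reference creatinine imputed to represent an eGFR of 75 should return 75 when put through the eGFR equation of the same plan. Here it does not. The reference is the denominator for AKI stage, so an upward shift means a patient needs a higher screening creatinine to count as Stage 2. Some borderline patients then drop out of an analysis that becomes confirmatory at two-sided 0.05 if both NICCE and CCPE succeed. The same shift lowers some Day 14 and Day 28 AKD stages. If the 37% loss is measured from a reference eGFR computed from the imputed creatinine, the pass limit also becomes more lenient than the nominal 75 implies.

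**Working it through.** **Inputs.** Code (SAP 4.1.4.1): constant 186, target 75, exponent −0.887, race factor 1.21. Forward equations (SAP 4.1.4.2 to 4.1.4.4): constant 175, exponent −1.154, race factor 1.212. Both use age^−0.203 and 0.742 for women.

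**The plan's own target, example: non-black man aged 55.** 55^−0.203 = 0.4433.
- As coded: t4 = 186 × 0.4433 = 82.46. Reference = (75/82.46)^−0.887 = 1.088 mg/dL.
- Forward with 186: 186 × 1.088^−1.154 × 0.4433 = 74.8. The code therefore reproduces 75, to rounding, under its own constant.
- Forward with the SAP's 175: 175 × 1.088^−1.154 × 0.4433 = 70.4. The target of 75 is not reproduced.

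**Consistent inverse.** The exact inverse of exponent −1.154 is −1/1.154 = −0.867. t4 = 175 × 0.4433 = 77.58. Reference = (75/77.58)^−0.867 = 1.030 mg/dL, which returns 75. Ratio 1.088/1.030 = 1.056.

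**Source of the gap.**
- Constant alone: (186/175)^(1/1.154) = 1.054.
- Exponent, like for like (−0.887 against −0.867): a factor of 1.002 for this man, and −0.6% to +0.8% over the grid below.
- Race factor: (1.212/1.21)^(1/1.154) = 1.001.

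**Range.** Over ages 30, 45, 55, 65 and 80, both sexes and both race terms, coded reference divided by consistent reference is 1.048 to 1.062. The coded reference returns an eGFR of 70.0 to 71.0 under the 175 equation.

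**Cut-offs for the man aged 55 (mg/dL).**

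| Quantity | Consistent (175) | As coded (186) |
|---|---|---|
| Reference | 1.030 | 1.088 |
| Stage 2, 2 × reference | 2.06 | 2.18 |
| Stage 3 by ratio, 3 × reference | 3.09 | 3.26 |
| 37% loss, only if measured from a reference eGFR computed with 175 | 1.54 | 1.62 |

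The last row uses 0.63^(−1/1.154) = 1.492 × reference. On that reading the eGFR limit is 0.63 × 70.4 = 44.4 instead of 0.63 × 75 = 47.25. The nominal 37% becomes a loss of 1 − 44.4/75 = 41% from 75, and 40–41% across the grid.

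**How many patients could move (assumption; the documents give no distribution).** Suppose screening creatinine divided by the consistent reference is lognormal with median 1.2 to 2.5 and log-SD 0.4 to 0.6. Those lost from Stage 2/3 on the ratio criterion lie between 2 and 2k, with k from 1.048 to 1.063. For median 2.0, log-SD 0.4 and k = 1.055, the share at or above the cut-off falls from 0.500 to 0.447, a loss of 0.053. Over the whole range the loss is about 2–6% of patients with imputed references, or about 5–24% of those who would otherwise enter on the ratio.

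**The case against.** **The code is coherent on its own terms.** Run forward with 186 it returns about 75, and the documents do not say which constant was intended. This stands: the defect is the mixture of versions, and "too high" means relative to the SAP's 175 equation. Staging compares creatinine with creatinine and never calls the 175 equation. Even so, the entry cut-off depends on which version supplies the reference, and the plan uses both versions under one name.

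**The exponents.** A reader might infer a second conflict between −0.887 and −1.154. One is an inverse exponent and the other a forward exponent. The proper comparison is −0.887 with −0.867, which is worth about 1% or less.

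**Who passes.** A reader might infer that the mismatch necessarily changes who passes the key secondary endpoint. The documents do not establish that. The formula in SAP 4.1.4.3 measures loss from screening eGFR and has no reference term, so the limit does not move. Under SAP 2.3 and 4.1.1, loss is taken from the reference eGFR, but no formula for that quantity is given. If it is simply the 75 being imputed, the limit stays at 47.25. Only if the imputed creatinine is converted with the 175 equation does it move. The conflict between these sections is separate and larger: for a patient at 2 × reference at screening, the failing Day 28 creatinine is 1.49 × reference under one rule and 2.98 × under the other.

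**Stage 3.** Moving a borderline Stage 3 patient to Stage 2 does not change entry, because both stages are included. Stage 3 by creatinine of at least 4 mg/dL or by renal replacement therapy does not depend on the reference.

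**Existing safeguards.** An adjudicated reference is already a planned sensitivity analysis for both stage and endpoint (SAP 4.1.4.2 and 8.11). That helps show robustness but leaves the primary determination as coded.

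**Inference.** A reader might fear bias between arms or an inflated error rate. The imputation is identical in both arms and uses pre-dose data, so neither follows.

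**Conclusion.** The mismatch is real and the arithmetic is firm. For patients with no usable historical creatinine, the imputed reference is about 5–6% above the value the SAP's own eGFR equation implies (4.8–6.2% over ages 30 to 80), and it returns about 70–71 where 75 was intended. Nearly all of this comes from 186 against 175.

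The established consequences are a higher Stage 2 entry cut-off for the key secondary analysis and shifted AKD stages at Days 14 and 28. An effect on the 37%-loss limit is conditional on how SAP 2.3, 4.1.1 and 4.1.4.3 are reconciled. What changes is the analysed population and, on one reading, the stringency of the endpoint, not type I error.

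The overall effect depends on the share of patients without a usable prior creatinine, which the documents do not give. The 2–6% figure for patients moved rests on the assumed distribution. The point is worth correcting because it is a rule that does not do what it is written to do, but it does not touch NICCE or CCPE.

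**What to change.** Before unblinding, use one MDRD version in both directions. Since all three forward formulas use 175, the natural edit in all four SAS blocks is `t4 = 175*t1*t2*t3`, with `t3 = 1.212` where `black=1`, and `Scrt = (75/t4)**(-1/1.154)`. Add a programmed check that each imputed reference returns 75 in the SAP 4.1.4.2 equation.

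First confirm which version ATB-203 uses. SAP 1.1 states that the AKI endpoints are harmonised with that trial, and its code is not visible here; a one-sided edit could break the match. If ATB-203 carries the same mixture, change both.

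Reconcile the definition of eGFR loss in SAP 2.3 and 4.1.1 with the formula in 4.1.4.3 as a separate item, and report how many patients had an imputed reference. The cost is a few constants and one check, with no new data; the main effort is coordination with ATB-203.
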